3.6 Endpoints

Primary endpoint

The proportion of antimicrobial prescriptions adherent with prescribing guidelines delivered by mobile phone app versus paper-based prescribing guidelines at month 16 (12 months' exposure in each group)

Secondary endpoints

1. Total antimicrobial defined daily doses (DDDs) prescribed in mobile phone app versus paper-based groups of 12 months' exposure in each group

2. Proportion of patients prescribed antimicrobials by the intravenous route in mobile phone app versus paper-based groups of 12 months' exposure in each group
3. AMS knowledge level of prescribers prescribed in mobile phone app versus paper-based groups of 12 months' exposure in each group
4. Prescriber satisfaction/acceptability of the prescribing guidelines in mobile phone app versus paper-based groups of 4 months' exposure in each group
5. Total costs of antimicrobial prescribed in mobile phone app versus paper-based groups of 12 months' exposure in each group
6. Proportion of patients admitted to hospital receiving an antimicrobial prescription before and after introduction of the paper-based prescribing guidelines; and the mobile phone app prescribing guidelines + AMS training of 12 months' exposure in each group

Definitions of adherence to the guidelines

1. Full adherence with the guidelines = using correct antimicrobial agent (s) and correct dose based on the provided antimicrobial prescribing guidelines
2. Partial adherence with the guidelines = using correct antimicrobial agent (s) with incorrect dose based on provided antimicrobial prescribing guidelines
3. Non-adherence with the guidelines = using a different antimicrobial agent (s) compared to that suggested in provided antimicrobial prescribing guidelines

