Study duration	16 months (four months preintervention period and 4-month interval between each step (three steps))
Sample size and power calculation	The sample size of six hospitals was estimated assuming 30% antimicrobial prescription adherence with the paper-based prescribing guidelines (reference), and assuming 0.05 intra-cluster correlation coefficient. This will have 80% power to be able to detect a 15% minimum difference in adherence after introduction of the mobile phone app prescribing guidelines (intervention) at a 0.05 significance level.
Randomization and blinding	Simple random sampling will be used to select the order (step) of interventions implementation for a group of hospitals (two hospitals per group and one group per step). Neither hospitals nor investigators will be blinded to the timing of intervention.
Intervention	A MicroGuide antimicrobial prescribing guideline mobile phone application and

	AMS training
Reference	Paper-based antimicrobial prescribing guidelines
Outcomes/Primary endpoint	The proportion of antimicrobial prescriptions adherent with prescribing guidelines delivered by mobile phone app versus paper-based prescribing guidelines at month 16 (12 months' exposure in each group)
Secondary endpoints	
 1. Total antimicrobial defined daily doses (DDDs) prescribed in mobile phone app versus paper-based groups after 12 months' exposure in each group 2. Proportion of patients prescribed antimicrobials by the oral route in mobile phone app versus paper-based groups after 12 months' exposure in each group 3. AMS knowledge level of prescribers prescribed in mobile phone app versus paper-based groups after 12 months' exposure in each group 4. Prescriber satisfaction/acceptability of the prescribing guidelines in mobile phone app versus paper-based groups after 4 months' exposure in each group 5. Total costs of antimicrobials prescribed in mobile phone app versus paper-based groups after 12 months' exposure in each group 6. Proportion of patients admitted to hospital receiving an antimicrobial prescription before and after introduction of the paper-based prescribing guidelines; and the mobile phone app prescribing guidelines + AMS training after 12 months' exposure in each group
Outcome measurement	
 • Point prevalence surveys (PPS) of hospital antimicrobial use • Prescriber questionnaires • AMS knowledge surveys of prescribers

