Data management	
Open Data Kit (ODK) system will be used as data collection instrument. We will collect data on patients' characteristics, antimicrobial prescription status, the frequency of use of the antimicrobial prescribing guidelines (both paper-based and mobile app), AMS knowledge level of prescribers, acceptability of the guidelines and the cost of antimicrobial prescriptions in both groups.
 
All data will be kept securely, protected by password access with automatic daily backup.

Statistical analysis	A logistic mixed-effects regression model will be used to compare the proportion of antimicrobial prescription adherence measured cross-sectionally at month 0, 4, 8, 12 and month 16 after introduction of prescribing guidelines delivered by mobile phone application versus paper-based. The model will compare all wedges in the intervention from month 4 to month 16 with all wedges in the reference arm from month 0 to month 12. The duration of exposure of each hospital to the reference or intervention arm will be included in the model as interaction term with the study arm in order to assess whether the duration of exposure is the effect modifier. The model will consider the correlation among the outcomes' measurements from the same hospital (cluster) by adjusting for clustering in the model. Odds ratios and the corresponding confidence intervals will be obtained and reported.
Ethics	University of Health Sciences, Vientiane, Lao PDR and Oxford Tropical Ethics Committee (OxTREC), University of Oxford, United Kingdom

Trial insurance	Provided by University of Oxford
Dissemination	1/ Quarterly and annual reports (PPS dashboard and paper report) to participating hospitals, Lao Ministry of Health 2/ Publication in national and international journals 3/ Oral presentation/poster in both national and international levels
Sponsor	University of Oxford
Funder	Wellcome Trust of Great Britain

I. Introduction

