3.4 Randomization and blinding

Six participating hospitals have been divided into 3 pairs based on the geographical location and convenience for conducting the surveys. The first paired hospitals include two provincial hospitals from the north of Laos (Luang Namtha and Xiengkhuang), the second pair includes hospitals in the center (Mahosot Hospital-central referral hospital and Vientiane provincial hospital which is 80 km from the center of the capital to the north). The third pair includes two provincial hospitals from the south of Laos (Savannakhet and Salavan).

As there are only 3 orders to be assigned, clusters will be randomly assigned to one of three start dates using a simple random sampling, to have access to the study intervention. Three paired hospitals (LNT+XK, MS+VTP and SVK+SV) will be written on three different paper slips (similar paper size and paper texture). All slips will be folded to the same size and put in the non-transparent container, covered firmly and mixed well. A person who is not related to the study will be asked to pick up the paper slip one by one and read out to the PI and a co-investigator. Simple random sampling processes will be performed before the start of the project and the order of each paired hospital to intervention introduction will be recorded. At month 4 after the start of the project, the intervention will be introduced to the first selected paired hospital, then every four months each pair of hospitals will be rolled out from the reference phase to the intervention phase until all have started the intervention. This will give 1:1 ratio of intervention vs reference period of observation (figure 2). We will therefore be able to compare the effects of the reference and intervention over a reasonable period of time. Neither hospitals nor investigators will be blinded to the introduction of the intervention.

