After the first paired hospital is randomly selected to have access to the mobile phone app prescribing guidelines at month 4, the second pair of hospitals will be randomly selected to have access to the mobile phone app at month 8, and the last pair of hospitals will have access to a mobile phone app at month 12 (Figure 2).

The order of activities at the start of the project are listed below (these activities will be applied to all six hospitals, one by one):

1. PPS on hospital antimicrobial use for all 6 hospitals (Appendix A1, A2 and A3)
2. AMS knowledge survey (Appendix A5)
3. Pre-prescribing guidelines survey (Appendix A9)
4. Access to paper prescribing guidelines for all 6 hospitals
5. Introductory session to paper prescribing guidelines (Appendix A6)
6. PPS reports (Appendix A4)

Activities in the reference phase after the start of the project (month 0) until the last paired hospital is assigned to the intervention (month 12) are listed below:

1. PPS on hospital antimicrobial use (Appendix A1, A2 and A3)
2. PPS reports (Appendix A4)

c. Intervention phase

c.1 Antimicrobial Prescribing guidelines mobile phone application (MicroGuide)

Both paediatric and adult antimicrobial prescribing guidelines will be transferred to [MicroGuide](#); which is a medical guideline application. MicroGuide was launched in 2013 and has been adopted by 114 medical organizations, with more than 100,000 users in 173 countries. MicroGuide is an offline application, free-of-charge for the individual users. The app can monitor the number of users and which guidelines are being accessed.

The app will be installed to the personal smart phones of local physicians by the PI. The project will not provide a smart phone to any physician without one (approximately <10% of physicians in provincial hospitals– unpublished data). The contents of the mobile app guidelines will be the same as the paper version but using hyperlinks to information, rather than displaying it as in paper guidelines. Both mobile app and paper guidelines will be available in Lao and English languages.

c.2 Antimicrobial stewardship (AMS) training

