measured cross-sectionally at month 0, 4, 8, 12 until month 16 after introduction of prescribing guidelines by mobile phone application versus paper-based (30). The model will compare all wedges in the intervention from month 4 to month 16 with all wedges in the reference arm from month 0 to month 12. The duration of exposure of each hospital to the reference or intervention arm will be included in the model as interaction term with the study arm in order to assess whether the duration of exposure is the effect modifier. The model will consider the correlation among the outcome's measurements from the same hospital (cluster) by adjusting for clustering in the model. Odds ratios and the corresponding confidence intervals will be obtained and reported. Tests of significance will be performed at 5% level. Analyses will be done using Stata 15.0 or higher. Likert scale analysis will be used to evaluate prescriber satisfaction with/ acceptability of paper-based compared to mobile phone app delivered antimicrobial prescribing guidelines. The satisfaction/acceptability scale will be assigned in six categories, including strongly agree=5, agree=4, neutral=3, disagree=2 and strongly disagree=1, no opinion/not use=0. Mann-Whitney test will be used to assess the differences between paper-based population and mobile phone app population. AMS knowledge level of prescribers will be assessed using questionnaires based on information in the prescribing guidelines. The overall proportion of correct answers in each time point will be compared (baseline, after paper-based guidelines (before AMS training and introduction of mobile phone app guidelines) and after AMS training and introduction of mobile phone app guidelines). Other factors such as extra AMR training program from hospital/MoH/other organizations, level of education and specialties of prescribers will also be taken into account.

Cost of antibiotic therapy will be calculated from the start date of treatment to the survey day. The unit costs for the antibiotics will be obtained from the [International Medical Product Price Guide](#).

Antibiotic defined daily dose (DDD) will be calculated using data (antibiotic agent, start date, dose and DDD of each antibiotic from www.whooc.no) from PPS in both IPD and OPD. Antimicrobial cost data from participating hospitals will also be collected each hospital pharmacy for comparison with international cost.

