Training date, time and venue: the session will take maximum 4±1 hours in total (including installation and registration step by step, also include discussion/questions). Training date, time and venue will be informed to all doctors one week in advance and again 3 days before starting the session. The session will be run in each hospital separately (2 hospitals on month 4, another 2 on month 8 and the last 2 hospitals on month 12) after conducting point prevalence survey (PPS) of hospital antimicrobial use. Verbal consent will be asked from participants to record each participant's name, age, sex, working position, department, years of work and phone number onto the session registration sheet.

Instructor: the principal investigator of the study will be the training instructor. Training will be given in the format of PowerPoint presentation and showing the real process of each step, followed by questions and discussion.

Training material: A handout of the training will be provided to all participants (the same standard session for all hospitals).

Training details: training session will include introduction to the MicroGuide, how to register, how to install, how to use step by step and how to update the App.

A8. Introductory (paper/App guidelines) session registration sheet

Introductory session of the use of therapeutic and prophylactic antimicrobial prescribing guidelines

Date: _____, Time: _____

Venue: _____, Hospital: _____

Participants list:

No.	Name and Surname	Age	Sex	position	Department	Year of graduation from medical school	Phone number
1							
2							
3							
4							
5							
6							
7							
8							
9							
10							
11							
12							
13							
14							
15							
16							
17							
18							
19							
20							
21							
22							
23							
24							
25							
26							
27							
28							
29							
30							

A9. Pre-prescribing guideline Survey

Pre-prescribing guideline Survey

Date: ___/___/____, Year of graduation from medical school: _____, Speciality: _____,
Department: _____ Hospital: _____

1. How frequently do you prescribe antimicrobial (s)?

Daily Nearly every day Weekly Monthly Never

2. How often do you access any antimicrobial prescribing guidelines?

Daily Nearly every day Weekly Monthly Never

3. Do you have a smart phone? Yes No Sometimes; If answer is "No", you do not have to answer question 4, 5 and 6

4. Do you carry your smart phone with you at work? Yes No

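### The primary endpoint's month 16 time point and 12 months' exposure in each group do not match the crossover schedule or the planned all-wedge model, and that model names no primary odds ratio

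*Combined protocol and SAP*

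**What the plan says.** The primary endpoint appears twice in the combined protocol and SAP. Section 3.6 has app versus "paper-based prescribing guidelines at month 16 (12 months' exposure in each group", and the Trial synopsis has app "versus paper-based prescribing guidelines at month 16 (12 months' exposure in each group". The 12-month phrase recurs in secondary endpoints 1, 2, 3, 5 and 6.

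The schedule is in section 3.5 and Figure 2. The first pair receives the app at month 4, the second at month 8, and "the last pair of hospitals will have access to a mobile phone app at month 12". Appendix A7 puts each app session after that round's survey: "2 hospitals on month 4, another 2 on month 8 and the last 2 hospitals on month 12) after conducting point prevalence survey (PPS". Section 3.4 adds: "This will give 1:1 ratio of intervention vs reference period of observation".

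The analysis does not isolate month 16. The synopsis says "The model will compare all wedges in the intervention from month 4 to month 16", and the Statistical analysis section sets "all wedges in the intervention from month 4 to month 16 with all wedges in the reference arm from month 0 to month 12". Duration of exposure is "included in the model as interaction term with the study arm in order to assess whether the duration of exposure is the effect modifier". No other model for adherence is described.

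The intervention is the app together with AMS training (synopsis, section 3.5 c.2, Figure 2), and the paper guidelines stay available after crossover (section 3.5 c.3, note b). The primary objective, primary endpoint and power statement name only the app.

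**The concern.** The primary endpoint is what the result will be judged against. Here its time point and exposure describe a comparison that the schedule does not supply and the analysis section does not plan. A reader could take the all-survey result for an effect after 12 months of use, or for an effect of the app format alone.

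The model raises a second question. With an arm-by-exposure interaction in the only stated model, several odds ratios can be read from one fit, and the plan does not say which is primary. Neither hospitals nor investigators are blinded to the timing of the intervention (section 3.4), which is a further reason to settle this before adherence data are seen.

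**Working it through.** **Inputs.** Crossover months 4, 8 and 12, two hospitals per pair, 16 months in total (sections 3.4 and 3.5). Surveys at months 0, 4, 8, 12 and 16. At each step the app follows the survey (section 3.5 c.3, Appendix A7), so a pair's first app survey comes four months after crossover.

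**1. Time in each condition.** Paper months = crossover month; app months = 16 − crossover month.

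| Pair | Paper | App |
|---|---|---|
| First | 4 | 12 |
| Second | 8 | 8 |
| Third | 12 | 4 |

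Paper: 2 × (4 + 8 + 12) = 48 hospital-months. App: 2 × (12 + 8 + 4) = 48. This reproduces the plan's 1:1 ratio. Twelve months in both conditions would need 12 + 12 = 24 months per hospital, against 16 available, so no hospital has both.

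**2. Hospitals in each phase at each survey.**

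| Month | Paper phase | App + AMS phase |
|---|---|---|
| 4 | 6 | 0 |
| 8 | 4 | 2 |
| 12 | 2 | 4 |
| 16 | 0 | 6 |

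At month 16 the paper column is empty.

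**3. Exposure behind the planned comparison.** App hospital-surveys at 4, 8 and 12 months' exposure number 6, 4 and 2, so 12 in all. Mean exposure, counting hospital-surveys equally, is (6×4 + 4×8 + 2×12)/12 = 80/12 = 6.7 months. Paper hospital-surveys at months 4, 8 and 12 also number 6, 4 and 2, with the same mean. If month 0 counts as reference there are 12 + 6 = 18, and the mean falls to 80/18 = 4.4 months. Twelve months is reached in 2 of 12 app hospital-surveys and in 2 of 12 (or 2 of 18) paper hospital-surveys.

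**4. What the interaction does to the arm odds ratio.** Let A = 1 for app and 0 for paper, and let D be months in the current condition, taken as linear for illustration:

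logit(p) = a + bA + cD + dAD + hospital effect.

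The app-versus-paper odds ratio at exposure D is exp(b + dD). With D counted from zero, the arm coefficient is b. Centred at 8 months it is b + 8d; centred at 12 months it is b + 12d. These agree only if d = 0. Omitting the main effect of D, or treating D as categories, leaves the same problem: the arm coefficient refers to the zero or baseline level chosen. On the natural zero, exp(b) describes an app effect at zero months, when no app survey is taken.

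**5. Month 0.** Section 3.5 b and its activity list put the first survey before the paper guidelines, and Figure 2 shows no paper label at month 0. Section 3.3 describes the baseline as following their introduction, and the analysis text starts the reference arm at month 0. This decides between 12 and 18 reference hospital-surveys.

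**6. Label.** AMS training is named in secondary objectives 1, 2, 3, 5 and 6 and in secondary endpoint 6. It is absent from the primary objective, primary endpoint and power statement. All 12 app hospital-surveys follow training, so the schedule does not separate the two components.

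**The case against.** The strongest defence is that the endpoint is shorthand. Paper is in use somewhere from month 0 to month 12 and the app from month 4 to month 16, two 12-month windows that match the analysis text and fit the 1:1 ratio. On that reading, month 16 may simply mean data accrued by the end of the trial, since section 3.3 has measurements continuing until then. This is plausible and takes much of the force out of the point. But the endpoint speaks of exposure in each group and does not mention windows, and a reader cannot recover the all-wedge comparison from it.

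The analysis sections also state the comparison openly and give the interaction's purpose. That stands. What they leave open is which odds ratio is the headline result.

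Three stronger readings are tempting, and the documents do not support them.

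- A reader might infer that the trial cannot deliver a primary result. It can: adherence is measured at every survey, and the all-wedge contrast is estimable.
- A reader might infer that the training is a hidden confounder. It is not hidden: the synopsis, section 3.5 and Figure 2 all present the intervention as app plus training. The app-only wording is a secondary labelling point.
- A reader might infer that the stated 80% power fails because a 12-month effect would be estimated less precisely. No 12-month test is planned, section 3.3 does not tie the power to one, and the documents give no number of prescriptions per survey from which to compute it. Power therefore plays no part in this point.

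**Conclusion.** The point holds as an inconsistency in the primary endpoint, with an unnamed primary estimate beside it. At month 16, none of the six hospitals is in the paper phase. This concerns trial phase, not access, because prescribers keep the paper guidelines. One pair of three reaches 12 months on the app, and a different pair reaches 12 months on paper. The planned comparison instead pools 4, 8 and 12 months of exposure, with a mean of 6.7 months at app surveys, and it concerns app plus AMS training added to paper versus paper alone.

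The counts rest only on the crossover schedule and on each survey preceding that step's app session. The mean exposure also weights hospital-surveys equally; weighting by prescriptions would change it by an amount the documents do not allow one to calculate. The interaction argument assumes a 0/1 arm code and that the term enters the model as the text describes. Both matters should be settled before adherence data are seen.

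**What to change.** 1. **Endpoint text (synopsis and 3.6).** Delete the month 16 and 12-month wording. Define the primary endpoint as the proportion of antimicrobial prescriptions adherent with the guidelines under app plus AMS training, with paper still available, versus paper alone, over all intervention and reference surveys as in the all-wedge model. In secondary endpoints 1, 2, 3, 5 and 6, replace the 12-month phrase with the surveys that supply each. Endpoint 3, for example, draws on the AMS knowledge survey, held three times per hospital.
2. **Primary odds ratio (both analysis texts).** Name one: the overall arm effect from the model without the interaction or, if the sponsor prefers, an exposure-averaged effect with its weights stated. Report the interaction model as the planned check of effect modification.
3. **Label.** Add AMS training to the primary objective, primary endpoint and power statement, so that conclusions concern the bundle.
4. **Month 0.** Reconcile sections 3.3 and 3.5, Figure 2 and the analysis text on whether this survey precedes paper or belongs to the reference arm, before listing the reference surveys.

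**Cost.** Visits, intervention, randomization and sample size are untouched. Items 1 and 3 are wording. Item 2 is a small analysis decision, because it takes the interaction out of the primary estimate or averages over it. Its downside is that one overall effect can hide a change with exposure, which the interaction model is kept to show. Item 4 may change the number of reference hospital-surveys from 18 to 12. The resulting claim is less specific than the present wording suggests.

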Although the severity of the AMR situation in Laos remains lower than elsewhere in Asia, misuse of antimicrobials is a major driver of resistance. This is a therefore an important opportunity for implementation of a simple technology, which may help reduce further worsening of the AMR situation. Antimicrobial prescribing apps are a promising tool to improve prescribing. However, there has been no evidence from trials to support whether the antimicrobial prescribing guidelines in the format of a mobile phone application are superior to conventional means (i.e. paper-based) in low- and middle-income countries (LMIC). This trial could have a significant impact in Laos and in other LMICs, and inform policy globally, by improving prescribing and hence reducing AMR.

II. Study objectives and hypothesis

Study objectives

Primary objective

To compare the proportion of antimicrobial prescriptions adherent with prescribing guidelines delivered by mobile phone application (app) versus paper-based prescribing guidelines in both in- and outpatients in six general hospitals in Laos

Secondary objectives

1. To compare the change in antimicrobial defined daily doses (DDDs) after introduction of paper-based versus mobile phone app prescribing guidelines plus antimicrobial stewardship (AMS) training in both in- and out patients

2. To compare the change in proportion of patients receiving intravenous antimicrobials route between paper-based and mobile phone app prescribing guidelines + AMS training in both in- and out patients
3. To compare the AMS knowledge level of the prescribers before and after prescribing guidelines delivered by mobile phone app and AMS training
4. To compare the prescriber satisfaction with/acceptability of paper-based prescribing guidelines versus mobile phone app prescribing guidelines
5. To compare antimicrobial costs before and after prescribing guidelines delivered by mobile phone app and AMS training in both in- and outpatient departments
6. To compare the proportion of patients admitted to hospital receiving an antimicrobial prescription before and after introduction of the paper-based prescribing guidelines; and the mobile phone app prescribing guidelines + AMS training

III. Methods

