3.2 Study sites

Six hospitals (two referral (200-450 beds) and four provincial hospitals (60-100 beds) have been purposively selected based on their capacity, location, previous participation in our PPS program with available hospital antimicrobial use and antimicrobial susceptibility data.

Mahosot Hospital (MS) has 450 beds and is a central referral hospital situated in Vientiane City in Laos (17°95'N 102°61'E, 268m above mean sea level). There are 968 staff, including 222 physicians,

414 nurses, 19 dentists, 46 pharmacists, 11 radiologists and 147 non-health worker staff. There are 18 in-patient wards and one main out-patient and small number of OPDs within in-patient wards.

Vientiane Provincial Hospital (VTP) has 100 beds. There are 211 staff, including 30 physicians, 99 nurses, 6 dentists and 9 pharmacists (data from 2018). There are six in-patient wards and one outpatient ward. The hospital is ~70km from Vientiane City (18°47'N 102° 48'E 497m above mean sea level).

[figure not shown]
Xiengkhuang Provincial Hospital (XK) has 150 beds. There are 305 staff, including 66 physicians, 117 nurses, 6 dentists and 24 pharmacists (data from 2019). There are 11 in-patient wards and one main out-patient units and a small number of OPDs within in-patient wards. It is in a broad valley in the northeast highlands (19° 27'N 103° 10'E, 1,150m above mean sea level).

Luang Namtha Provincial Hospital (LNT) has 50 beds. There are 117 staff, including 18 physicians, 36 nurses, 3 dentists and 10 pharmacists (data from 2018). There are 6 in-patient wards and OPDs within in-patient wards. It is in the highlands on the China and Myanmar borders in the far NW of Laos (21° 00'N 101° 24' E; 570m above mean sea level)

Savannakhet Provincial Hospital (SVK) has 200 beds. There are 293 staff, including 60 physicians, 139 nurses, 7 dentists and 13 pharmacists (data from 2019). There are 9 in-patient wards and one main out-patient and small number of OPDs within in-patient wards. It is located in the southern part of the country in the largest province in Laos (16° 55'N 104° 74'E; 726 m above mean sea level)

Salavan Provincial Hospital (SV) has 70 beds. There are 191 staff, including 30 physicians, 50 nurses, 3 dentists and 11 pharmacists (data from 2018). There are 7 in-patient wards and OPDs within in-patient wards outpatient. It is on the western slopes of Annamite mountains in southern Laos (15°43'N 106°25' E; 184m above mean sea level).

Figure 1. SW-CRCT study sites

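### Secondary endpoints 1 and 5 are worded as group totals of DDDs and cost with no denominator, effect measure or model, and the counting window fails for outpatient cost and is left open for DDDs

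*Combined protocol and SAP*

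**What the plan says.** Section 3.6 words endpoint 1 as "Total antimicrobial defined daily doses (DDDs) prescribed in mobile phone app versus paper-based groups" and endpoint 5 as "Total costs of antimicrobial prescribed in mobile phone app versus paper-based groups". The trial synopsis agrees: "Total costs of antimicrobials prescribed in mobile phone app versus paper-based groups after 12 months". The objectives in section II are phrased differently. Objective 1 is "To compare the change in antimicrobial defined daily doses (DDDs) after introduction of paper-based versus mobile phone app prescribing guidelines", and objective 5 is "To compare antimicrobial costs before and after prescribing guidelines delivered by mobile phone app and AMS training in both in- and outpatient departments".

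The statistical analysis section gives a logistic mixed model with odds ratios for adherence, a Mann-Whitney test for satisfaction and a comparison of correct answers for AMS knowledge. For DDDs and cost it gives only inputs and price sources. Cost runs from the start of treatment up to the survey day. The DDD sentence lists agent, start date, dose and reference DDD, but not where counting stops.

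On balance between groups, section 3.4 says: "This will give 1:1 ratio of intervention vs reference period of observation".

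Denominators are collected for another purpose, the proportion of patients prescribed an antimicrobial: in-patients on the ward at 08:00 (section 3.7, a.1) and outpatient consultations from the logbook (a.2). Outpatient form A3 has a survey date and a stop date but no start date, although section 3.7 lists a start date among the data for both settings.

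**The concern.** A group total depends on how many patients the group contains as well as on how they are treated. In this stepped wedge the pairs differ in size and spend different numbers of surveys in each condition. A pooled total could therefore show a saving or an excess that reflects only which pair switched first.

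The counting window raises a separate problem. Outpatient prescriptions are captured on the day they are issued, so a rule that stops at the survey day leaves out nearly all of the course. A change in outpatient course length, which a prescribing guideline might well produce, could not appear in the cost endpoint. For DDDs, an analyst would have to choose between a daily and a cumulative count with the data in hand, in a trial whose investigators are not blinded.

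**Working it through.** **1. The plan's 1:1 ratio.** Section 3.5 (c.3) places each survey before the app is introduced, and Figure 2 agrees. Hospital-surveys at months 4, 8, 12 and 16:
- paper: 6 + 4 + 2 + 0 = 12
- app: 0 + 2 + 4 + 6 = 12

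The 1:1 ratio is reproduced, in hospital-surveys.

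**2. The same table weighted by size.** Beds are from section 3.2 (for example "Mahosot Hospital (MS) has 450 beds") and the pairs from section 3.4:
- North (N): 150 + 50 = 200
- Centre (C): 450 + 100 = 550
- South (S): 200 + 70 = 270

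With identical use per bed in both conditions:
- app = 3 × first + 2 × second + 1 × third
- paper = 1 × first + 2 × second + 3 × third

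| Order | App | Paper | App/paper |
|---|---|---|---|
| C-S-N | 2390 | 1690 | 1.41 |
| C-N-S | 2320 | 1760 | 1.32 |
| S-C-N | 2110 | 1970 | 1.07 |
| N-C-S | 1970 | 2110 | 0.93 |
| S-N-C | 1760 | 2320 | 0.76 |
| N-S-C | 1690 | 2390 | 0.71 |

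Three equal pairs would give 6/6 = 1.00, and so would a rate per bed or per patient in every order. The drawn order is not in the documents.

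**3. Sensitivity to the size measure.** Physicians per pair (section 3.2) are 66 + 18 = 84, 222 + 30 = 252 and 60 + 30 = 90. The extremes are 684/1020 = 0.67 and 1020/684 = 1.49. Section 3.2 also describes "four provincial hospitals (60-100 beds", which does not fit the 150 and 50 beds listed for the northern pair. Setting these to 100 and 60 (160 in all) gives 1570/2350 = 0.67 to 2350/1570 = 1.50.

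**4. Outpatient cost window.** For a course of L days issued on the survey day, counting that day as one, the uncounted share is 1 − 1/L. Course lengths are assumed:
- L = 3: 67%
- L = 5: 80%
- L = 7: 86%
- L = 10: 90%

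If days are counted as elapsed time, nothing is counted and the share is 100%. The plan does not say which convention applies.

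**5. Why the in-patient DDD window must be stated.** Assume constant treatment starts, census and daily dose, and let course length fall from 7 to 5 days.
- Survey-day DDDs scale with L: 5/7 = 0.71, or −29%.
- Start-to-survey-day totals, counted inclusively, scale with L(L+1)/2: 15/28 = 0.54, or −46%.
- With elapsed days they scale with L(L−1)/2: 10/21 = 0.48, or −52%.

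The daily and cumulative readings are different outcomes.

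**The case against.** The strongest reply is that nobody has announced a pooled sum. Objective 1 speaks of a change and objective 5 of a comparison before and after, so a within-hospital comparison may be intended. Fixed hospital size would then drop out. This stands in part: the 0.71 to 1.41 range is conditional on following the endpoint wording. But the within-hospital analysis is not written down. It would have to be expressed per survey, because a hospital in the first pair has one paper and three app surveys after baseline. It would also leave changes in patient volume and time trends uncorrected.

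A second reply is that the in-patient cost rule is stated and workable. It is, and this point does not ask for it to be replaced.

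A third is that the missing start date on form A3 is clerical, since outpatient prescriptions are issued on the survey day and the form records that date. That is fair. The text and the form should be reconciled, but no information is lost.

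A reader might also infer that stop dates will be documented more often under the app, because form A11 asks whether the app encourages recording of duration. Form A10 asks the same of the paper guidelines, and both items concern hospital charts rather than outpatient prescription sheets. The forms give no evidence of a difference by arm.

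**Conclusion.** The concern holds for two secondary endpoints and should be fixed. It goes beyond missing detail: the quantity as worded and the cost rule as written would both mislead if followed.

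- **Pooled totals.** With no effect, the app/paper ratio is 0.71 to 1.41 by order, and 0.93 or 1.07 if the centre pair is second. This assumes pooling, equal use per bed, and beds as a proxy for volume. Beds say little about outpatient volume.
- **Outpatient cost.** At least 67% of a course is uncounted for assumed courses of three days or more, and a change in course length cannot show.
- **DDDs.** The end of the counting window is not stated.

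A reader might infer that month 0 belongs to the paper group, since the adherence model describes its reference arm as beginning there. That would make the split 12 app to 18 paper hospital-surveys and give lower ratios in every order. The documents mostly point the other way. Section 3.3 sets the baseline survey apart from the four outcome measurements. Section 3.5 (b) places the month 0 survey before the paper guidelines and starts the reference period after their introduction. Figure 2 shows no paper guideline in its month 0 cells. The adherence model does not govern DDDs or cost. One sentence should remove the remaining doubt.

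The primary endpoint is unaffected.

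**What to change.** - **Definition.** For each hospital and survey, report DDDs and cost per 100 in-patients present at 08:00 and per 100 outpatient consultations, with the two settings kept separate.
- **Analysis.** Estimate an app:paper ratio with a confidence interval from a model with hospital, survey-period and arm terms. State that month 0 is a pre-guideline baseline and not paper-arm exposure.
- **Outpatients.** Compute cost and DDDs over the prescribed course, from the survey (prescription) date to the A3 stop date. Set the rule for missing stop dates before analysis and report the number missing by arm. Add DDDs per prescribed day, which need no stop date.
- **In-patients.** Keep the stated cost rule. State whether DDDs are daily or cumulative. Report survey-day DDDs and cost alongside, because start-to-survey-day totals depend on time already on treatment.
- **Dates.** Reconcile the outpatient start date in section 3.7 with form A3.

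The cost is revised wording and a little more analysis work, since both denominators and the stop-date field already exist. The downside is that some outpatient stop dates may be missing. Scanned prescription sheets are destroyed within one month, so a date not extracted by then cannot be recovered from the scan.
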